## **Protocol Deviation Reporting Requirements for Commercially Sponsored Research**

Sponsored research agreements may require the PI to notify the sponsor of all unplanned deviations or departures from IRB approved protocol procedures. Sponsor reporting requirements for deviations may differ from JHM IRB reporting requirements. It is the PI's responsibility to comply with the reporting requirements outlined in the signed contract.

## **8.0 STATISTICAL ANALYSIS PLAN**

### **8.1 Statistical Analysis Plan Summary**

This multi-center, nonrandomized, open-label Phase II study will enroll two cohorts of patients: 1) Cohort 1: relapsed/refractory AML, and 2) Cohort 2: newly diagnosed AML in older ( $\geq 65$  years) patients not candidates for induction chemotherapy.

### **8.2 Statistical Analysis Plan**

#### **8.2.1 Safety Run-In**

Each cohort will be enrolled separately with distinct null hypotheses and statistical plans. Since azacitidine and pembrolizumab have not been tested previously in combination in AML patients, we plan first to start enrollment with Cohort 1 (a safety run-in phase). Recognizing that Cohort 1 may also include patients who relapsed after allogeneic hematopoietic stem cell transplant (alloHSCT) and thus may have differential sensitivity (tolerability, immune-related adverse events [IRAEs]) to this drug combination, we will start enrollment in Cohort 1 to include patients who did not have prior alloHSCT.

The primary objective of the safety run-in is to determine the safety and tolerability of AZA followed by pembrolizumab in relapsed and refractory AML using a 3+3 design. We plan to monitor for DLTs in cycles 1, 2 and 3 as some of immunological side effects associated with pembrolizumab may occur with the delay. The first three patients will be enrolled and receive planned azacitidine and pembrolizumab in cycle 1. If 0 or 1 patient of the first three patients has a DLT (dose limiting toxicity) in cycle 1, we will enroll an additional 3 patients to better assess for toxicities. If less than 2 among first 6 patients experiences DLT in the cycle 1-3, we will open enrollment in Cohort 1 for all relapsed/refractory patients including those with prior history of alloHSCT and will also start to enroll patients in Cohort 2. If  $\geq 2$  of the first 3 patients or  $\geq 2$  of 6 patients have DLTs during cycle 1, we will perform safety (detailed toxicity) review to assess for disease versus treatment-related toxicities. Given that pembrolizumab is given only once in cycle 1 (day 8), we will first dose de-escalate azacitidine as detailed in Section 2.2. However, if the safety data analysis suggests that the toxicities are more likely pembrolizumab related, an alternative approach we may take is to exclude pembrolizumab in cycle 1 and start pembrolizumab dosing in cycle 2 when AML is better controlled but maintain azacitidine dose/schedule as described in Section 2.2. If

$\leq 1$  of the 6 patients experience DLTs during cycle 1 but  $\geq 2$  of 6 patients experience DLTs during cycle 2 and cycle 3, or cycle 1, 2 and 3, we will first dose de-escalate pembrolizumab as described in Section 2.2 and maintain azacitidine dose/schedule. When each dose de-escalation occurs (maximum 2), additional 6 patients will be enrolled at that dose level. For the details of dose de-escalation, please see Section 2.1 and 2.2 Trial Diagram.

Only after a safe dose/schedule is defined will we start enrollment in the phase 2 cohorts. A full safety assessment of the combination of AZA and pembrolizumab will be performed in all patients after 1, 2 and 3 cycles and in subsequent cycles according to the NCI Common Terminology Criteria for Adverse Events (CTCAE), version 4.0. Patients who are treated at dose/schedule selected for Phase 2 will be included in the primary efficacy analysis and the analyses of secondary and exploratory objectives.

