If  $\geq 2$  of the first 3 patients or  $\geq 2$  of 6 patients have DLTs during cycle 1, we will perform safety (detailed toxicity) review to assess for disease versus treatment-related toxicities. Given that pembrolizumab is given only once in cycle 1 (day 8), we will first dose de-escalate azacitidine to 75 mg/m^2 x 5 days. However, if the safety data analysis suggests that the toxicities are more likely pembrolizumab related, an alternative approach we may take is to exclude pembrolizumab in cycle 1 and start pembrolizumab dosing in cycle 2 when AML is better controlled but maintain azacitidine dose/schedule. If  $\leq 1$  of the 6 patients experience DLTs during cycle 1 but  $\geq 2$  of 6 patients experience DLTs during cycle 2 and cycle 3 or cycle 1, 2 and 3, we will first dose de-escalate pembrolizumab to 200 mg given every 4 weeks starting on Day 1 of Cycle 2 and maintain azacitidine dose/schedule. When each dose de-escalation occurs, additional 6 patients will be enrolled at that dose level. For the details of dose de-

[figure not shown]
escalation, please see Section 2.2 Trial Diagram.

Only after safe dose/schedule is defined ( $\leq 1$  of 6 patients having DLT in cycle 1-3) we will start enrollment in the phase 2 cohorts. A full safety assessment of the combination of AZA and pembrolizumab will be performed in all patients after 1, 2, and 3 cycles and in subsequent cycles according to the NCI Common Terminology Criteria for Adverse Events (CTCAE), version 4.0. For efficacy analysis, those patients who were treated at dose/schedule selected for Phase 2 will be included.

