### 3.3 Secondary Objective(s) & Hypothesis(es)

(1) **Objective (Cohort 1):** Characterize the toxicity of AZA followed by pembrolizumab in relapsed and refractory AML.

**Hypothesis:** AZA followed by pembrolizumab will be safe and tolerable when administered to relapsed and refractory AML patients.

(2) **Objective (Cohort 2):** Characterize the toxicity of AZA followed by pembrolizumab in older ( $\geq 65$  years) newly diagnosed AML patients not candidates for intensive induction chemotherapy.

**Hypothesis:** AZA followed by pembrolizumab will be safe and tolerable when administered to older ( $\geq 65$  years) newly diagnosed AML patients not candidates for intensive induction chemotherapy.

(3) **Objective (Cohort 1):** Assess the overall response rates [ie. CR/CRI/partial response (PR)/morphologic leukemia-free state (MLFS)/hematologic improvement (HI)] of AZA followed by pembrolizumab in relapsed/refractory AML patients.

**Hypothesis:** AZA followed by pembrolizumab will lead to a promising overall response rate in relapsed and refractory AML patients.

(4) **Objective (Cohort 2):** Assess the overall response rates [ie. CR/CRI/partial response (PR)/morphologic leukemia-free state (MLFS)/hematologic improvement (HI)] of AZA followed by pembrolizumab in newly diagnosed AML patients not candidates for intensive induction chemotherapy.

**Hypothesis:** AZA followed by pembrolizumab will lead to a promising overall response rate in older ( $\geq 65$  years) newly diagnosed AML patients not candidates for intensive induction chemotherapy.

(5) **Objective (Cohort 1 and Cohort 2):** Estimate disease-free survival (DFS) and overall survival (OS) of patients who achieve a CR/CRI for each cohort separately: relapsed/refractory (Cohort 1) and newly diagnosed older AML patients (Cohort 2).

**Hypothesis:** Patients who achieve a CR/CRI will have durable responses.

(6) **Objective (Cohort 1 and Cohort 2):** Estimate progression-free survival (PFS), time to progression (TTP), and OS for all patients. These survival parameters will be estimated separately for each Cohort.

**Hypothesis:** AZA followed by pembrolizumab will lead to a promising PFS, TTP and OS in both relapsed/refractory and older newly diagnosed AML patients not candidates for intensive induction chemotherapy.

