#### 4.2.3.1.2 Secondary Endpoints

- Characterize the toxicity of AZA followed by pembrolizumab in each Cohort (summary statistics). The toxicity will be classified and graded according to National Cancer Institute's (NCI) Common Terminology Criteria for Adverse Events (CTCAE, version 4.0)
- The overall response rate CR+CRi+partial response (PR)+ morphologic leukemia-free state (MLFS)+hematologic improvement (HI) (separately for each Cohort) as defined by the International European LeukemiaNet Guidelines in AML and IWG Modified Response Criteria (2006) for MDS (for definition of HI).
- Disease-free survival and overall survival of patients who achieve a CR/CRi for each Cohort separately. DFS will be defined as the time from CR/CRi to either relapse, death or last follow-up date (censored). OS will be defined as the time from study initiation to either death or last follow-up date (censored).
- Estimate progression free survival, time to progression, and overall survival for all patients (separately for each Cohort). PFS will be defined as the time from study initiation to progression or death or last follow-up date (censored).

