### 8.2.4 Analysis of Secondary Endpoints

The toxicity of AZA followed by pembrolizumab in 1) relapsed/refractory AML patients, and 2) older ( $\geq 65$  years) newly diagnosed AML patients not candidates for intensive induction chemotherapy will be described separately for each cohort using summary statistics.

The overall response rate, defined as CR/CRI/partial response (PR)/ morphologic leukemia-free state (MLFS)/hematologic improvement (HI) of AZA followed by pembrolizumab, will be estimated for each cohort separately and reported with exact 95% confidence intervals.

Disease-free survival (DFS) and overall survival (OS) will be estimated and plotted for patients who achieve a CR/CRI, separately by cohort, using the Kaplan Meier method. DFS will be defined as the time from CR/CRI to either progression, relapse, death (event) or last follow-up date (censored). OS will be defined as the time from study initiation to either death (event) or last follow-up date (censored).

Progression-free survival (PFS), time to progression, and OS will be estimated and plotted for all patients, separately by cohort, using the Kaplan Meier method. PFS will be defined as the time from study initiation to progression or death (event) or last follow-up date (censored). The cumulative incidence of progression will be estimated for each cohort (Prentice RL and Kalbfleisch JD. The

analysis of failure times in the presence of competing risks, *Biometrics*, 34: 541-554. 1978). Death will be considered a competing risk for progression.

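### Sections 2.1 and 8.2.1 differ on whether the Phase 2 dose restriction reaches the Cohort 1 toxicity summary, and 8.2.4 names no safety population

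*Combined protocol and SAP*

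**What the plan says.** Two sections state who enters the analyses after the safety run-in.

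- Section 2.1: "For efficacy analysis, those patients who were treated at dose/schedule selected for Phase 2 will be included".
- Section 8.2.1: patients at the dose/schedule chosen for Phase 2 "will be included in the primary efficacy analysis and the analyses of secondary and exploratory objectives".

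Toxicity is among the secondary objectives. Objective 3.3(1) is to "Characterize the toxicity of AZA followed by pembrolizumab in relapsed and refractory AML", and the first secondary endpoint in 4.2.3.1.2 is to "Characterize the toxicity of AZA followed by pembrolizumab in each Cohort (summary statistics"). Section 8.2.4 says that toxicity "will be described separately for each cohort using summary statistics". It does not say which patients form the denominator.

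Two further statements bear on the point. Just before its analysis-set sentence, 8.2.1 provides that "A full safety assessment of the combination of AZA and pembrolizumab will be performed in all patients after 1, 2 and 3 cycles", and it continues the assessment in later cycles. The run-in also has its own safety aim: "The primary objective of the safety run-in is to determine the safety and tolerability of AZA followed by pembrolizumab in relapsed and refractory AML".

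**The concern.** A dose level is abandoned in the run-in because of its toxicity: at least 2 patients with DLTs among 3 or 6 (5.2.1.3, Table 3). If the toxicity summary then covers only patients at the level that was kept, the analysis set has been chosen by the outcome being summarised. The summary would show the tolerability of the surviving level and leave out patients who received the same combination at a level with more DLTs. Such a selection is reasonable for efficacy, where the question is the response rate at the dose taken forward. It is not reasonable for a description of the combination's toxicity in relapsed/refractory AML. With two sentences of different reach and no safety population in 8.2.4, an analyst could build the table either way and cite the plan for it.

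**Working it through.** The plan gives no figure on this point to reproduce. The check is a comparison of text, then a count of the patients who could be concerned.

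**1. Text.** The two sentences make the same selection (patients at the chosen dose/schedule) but attach it to different analyses. Section 2.1 names efficacy. Section 8.2.1 names primary efficacy, secondary and exploratory objectives, and does not exempt toxicity. Because 8.2.4 is silent, the 8.2.1 sentence is the only analysis-set statement that reaches the toxicity summary.

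**2. Patients concerned.** Inputs: at most 2 de-escalations with 6 further patients at each new level (8.2.1); a level can fail on its first 3 patients or on 6 (Table 3); Cohort 1 maximum of 40 (1.0), reached (5.1.1). The documents do not say whether patients on an abandoned level count within the 40, so both cases are shown.

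| Patients on abandoned levels | Additional to 40 | Within 40 |
|---|---|---|
| 3 (starting level fails on first 3) | 3/43 = 7.0% | 3/40 = 7.5% |
| 6 (starting level fails on 6) | 6/46 = 13.0% | 6/40 = 15% |
| 12 (two levels of 6 fail) | 12/52 = 23.1% | 12/40 = 30% |

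By rule, a full level of 6 that fails has an observed DLT share of at least 2/6 (33%), and the accepted level has at most 1/6 (17%). That contrast restates the decision rule and does not estimate bias.

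**3. Chance that the starting level is abandoned.** With per-patient DLT probability p over cycles 1-3 (assumed), P(at least 2 of 6) = 1 − (1 − p)^6 − 6p(1 − p)^5:

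- p = 5%: 3.3%
- p = 10%: 11.4%
- p = 20%: 34.5%
- p = 30%: 58.0%
- p = 40%: 76.7%

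**4. Illustrative effect on a reported proportion.** Assume 40 patients in all, q = the DLT rate at the kept level, and the minimum DLT count on each failed level of 6. The all-treated rate is (DLTs on abandoned levels + q × remaining patients)/40; the restricted summary reports q.

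- q = 10%, 6 left out with 2 DLTs: (2 + 0.10 × 34)/40 = 13.5%, against 10.0% reported.
- q = 10%, 12 left out with 4 DLTs: (4 + 0.10 × 28)/40 = 17.0%, against 10.0%.
- q = 20%, 6 left out with 2 DLTs: (2 + 0.20 × 34)/40 = 22.0%, against 20.0%.
- q = 20%, 12 left out with 4 DLTs: (4 + 0.20 × 28)/40 = 24.0%, against 20.0%.

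**5. Which objectives.** Cohort 2 opens only after a safe dose/schedule is defined (2.1, 8.2.1), so no Cohort 2 patient can be on a level abandoned in the run-in. Only 3.3(1) can be affected, not 3.3(2).

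**The case against.** The strongest reply is that the plan never excludes anyone. The 8.2.1 sentence says who is included and does not say that nobody else is. It may simply confirm that run-in patients at the chosen dose count towards Phase 2. The sentence before it requires a CTCAE safety assessment in every patient. Section 8.2.3 names a dose-restricted set explicitly for pooled CR/CRi, whereas 8.2.4 describes toxicity by cohort with no dose condition. The stopping rule in 8.2.2.1 has none either, and 10.5 asks for toxicity data from the whole trial in the periodic reports.

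Part of this stands. A reader might infer that patients on an abandoned level vanish from the trial's toxicity results altogether. The documents do not support that: their DLTs are evaluated under the run-in's primary objective, and their safety assessments continue. What is at stake is the secondary summary in 8.2.4.

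The rest does not remove the conflict. The 2.1 sentence also lacks a limiting word, yet it plainly selects; the 8.2.1 sentence has no function unless it selects too. The all-patient sentence provides for assessment during treatment and does not define the denominator in 8.2.4. Stopping-rule counts and oversight reports are not that summary. Nor does the DLT evaluation replace it: 5.2.1.3 counts only one hematologic event as dose-limiting and excludes fever, infections, fatigue, bleeding and bone pain.

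The reply is also right that the practical effect may be nil. Sections 2.1, 5.2 and 5.2.2 still give the starting schedule as trial treatment, and none of the visible amendment summaries reports a reduced Phase 2 dose.

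**Conclusion.** The point holds as an inconsistency of minor severity. Sections 2.1 and 8.2.1 disagree on whether the dose restriction goes beyond efficacy, and 8.2.4 does not settle it. Followed literally, 8.2.1 would leave Cohort 1 patients on a toxicity-abandoned level out of the secondary toxicity summary: 3 to 12 patients, or 7% to 23% if additional to 40 and 7.5% to 30% if within the 40.

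These sizes are conditional on at least one de-escalation. The documents do not report the run-in's outcome. The unchanged starting schedule suggests that none occurred, but that is inference. A reader might take the percentages, or the shifts in the illustration, as bias present in this trial; the documents do not support that, and the DLT rates used are assumptions. Cohort 2 toxicity is not affected.

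**What to change.** Reword the last sentence of 8.2.1 to match 2.1, so that the restriction to the selected dose/schedule covers the efficacy analyses (primary and secondary) and the exploratory response analyses only. In 8.2.4, state that toxicity is summarised in every patient who received any azacitidine or pembrolizumab, by cohort, by assigned dose level and overall. If no de-escalation took place, the report can say so in a line and the dose-level column collapses to one.

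The cost is one or two sentences in the SAP and one table column. No treatment rule, sample size or additional data collection is involved, and the change can be made although accrual is closed.

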### 8.2.2 Sample Size

The primary objective of this study is to estimate the complete response (CR/CRi) rate in each cohort. We estimated sample sizes for the 2 cohorts using a one-sample, one-sided binomial test, with Type I and Type II errors of 0.05 and 0.2, respectively. For Cohort 1, the null and expected response rates were taken to be 0.1 and 0.25, respectively. For Cohort 2, the null and expected response rates were taken to be 0.17 and 0.34, respectively. The sample sizes were calculated to be 38 (which will be rounded to 40) and 40 for Cohorts 1 and 2, respectively.

We used an efficient and flexible design based on Bayesian predictive probability (Lee and Liu, 2008). This design controls the type I and type II error rates and also allows flexible monitoring for futility and efficacy of the new treatment. Furthermore, this design also has better sampling properties than Simon's 2-stage design, i.e. probabilities of early termination for futility under the null hypothesis and for efficacy under the alternate hypothesis are higher and the expected sample size is lower than Simon's 2-stage design.

The following input parameters were assumed in our design: minimum and maximum number of patients was 10 and 40, respectively. Type I and II errors were 0.1 and 0.2, respectively. For cohort 1, the treatment effect for current standard was 0.1 (i.e., probability of CR/CRi) and expected treatment effect for the new treatment was 0.25. For cohort 2, the treatment effect for current standard was 0.17 and expected treatment effect for the new treatment was 0.34. A beta (0.25, 0.75) distribution was assumed for the prior for the expected effect of the new treatment. This is a weak prior, which has negligible effect on the stopping boundaries.

The stopping boundaries for futility are given in the tables below for cohorts 1 and 2. For example, the first row of Table 1 indicates that we would stop the trial for futility if we see 0 responses (CR/CRi) out of the first 10 patients after 6 cycles of therapy (to be evaluable for futility pts must complete at least 2 cycles of therapy); if the study was not stopped after 10 patients, the next evaluation will be done after 14 patients (2nd row). Study will be stopped for futility if we see 1 response or less for futility. If the study continues, the next evaluation happens after 21 patients (3rd row). Study will be stopped if we see 2 or fewer responses in the first 21 patients.

Cohort 1: Interim monitoring boundaries for stopping for futility.

Patient. No.	Futility boundary (less than or equal to)
10	0
14	1
21	2
27	3
32	4
36	5
40	6

Cohort 2: Interim monitoring boundaries for stopping for futility.

Patient. No.	Futility boundary (less than or equal to)
10	0
11	1
16	2
20	3
24	4
27	5
31	6
34	7
36	8
39	9
40	10

For cohort 1, the expected sample size under the null and alternative hypotheses is 17.7 and 18.3, respectively. For cohort 2, these were 19.2 and 21.0.

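### Section 8.2.2 sizes the cohorts at one-sided alpha 0.05 but builds the monitored design at 0.10 without explanation, and its expected sample sizes need an efficacy stop that the plan never prints

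*Combined protocol and SAP*

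**What the plan says.** All of this is in section 8.2.2 of the combined protocol and SAP.

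- **Sizing.** The cohorts were sized "using a one-sample, one-sided binomial test, with Type I and Type II errors of 0.05 and 0.2, respectively", with null and expected CR/CRi rates of 0.10 and 0.25 (Cohort 1) and 0.17 and 0.34 (Cohort 2). The results are 38, rounded to 40, and 40.
- **Monitored design.** The inputs to the Bayesian predictive-probability design are then listed: "minimum and maximum number of patients was 10 and 40, respectively", and "Type I and II errors were 0.1 and 0.2, respectively". The rates are unchanged, and the prior is beta(0.25, 0.75).
- **Efficacy stopping.** It appears only as a general merit of the design compared with a Simon two-stage design: "probabilities of early termination for futility under the null hypothesis and for efficacy under the alternate hypothesis are higher".
- **Boundaries.** The worked example concerns futility only (after 10 patients, "the next evaluation will be done after 14 patients"). The first table is titled "Cohort 1: Interim monitoring boundaries for stopping for futility", and the Cohort 2 table has the same form.
- **Expected size.** "For cohort 1, the expected sample size under the null and alternative hypotheses is 17.7 and 18.3, respectively". The corresponding pair for the newly diagnosed cohort is given as 19.2 and 21.0.

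**The concern.** Two things do not fit together.

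First, one primary endpoint carries two type I error rates, and no sentence says which applies to what. A reader who takes 0.05 with 80% power as the property of this design would be misled if the monitored rule does not deliver it.

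Second, expected sample sizes of 18.3 and 21.0 when the treatment works are far too small for a design that stops only for futility. Such a design should usually run to 40 when the drug is active. Either an efficacy stop exists and has been left out, or the figures describe a different design.

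At stake are the planned size when the treatment works (18 to 21 patients per cohort, or 36 to 37), the response count that is a success, and the type I error and power attached to it. The plan gives no error rates for the rule as printed. By contrast, section 8.2.2.1 gives the toxicity rule explicit cut-offs, stopping probabilities and average sample sizes.

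**Working it through.** **Inputs** (all from 8.2.2). Rates p0/p1 are 0.10/0.25 and 0.17/0.34; minimum n is 10 and maximum 40. Futility stops, written n:count, apply at that count or fewer.
- Cohort 1: 10:0, 14:1, 21:2, 27:3, 32:4, 36:5, 40:6.
- Cohort 2: 10:0, 11:1, 16:2, 20:3, 24:4, 27:5, 31:6, 34:7, 36:8, 39:9, 40:10.

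**1. The plan's sample sizes.** The formula is not stated, but the arcsine approximation reproduces them: n = [(z0.95 + z0.80) / (2 asin√p1 − 2 asin√p0)]².
- Cohort 1: [2.4865 / (1.0472 − 0.6435)]² = 37.9, so 38.
- Cohort 2: [2.4865 / (1.2451 − 0.8500)]² = 39.6, so 40.

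At alpha 0.10 the same formula gives 28 and 29, so 0.05 is not a misprint.

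**2. Exact binomial test at 0.05, fixed n=40.**

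| | Success at | Exact type I | Power | Smallest n with 80% power |
|---|---|---|---|---|
| Cohort 1 | ≥8 | 0.0419 | 0.818 | 40 |
| Cohort 2 | ≥12 | 0.0301 | 0.755 | 42 |

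**3. Success counts implied by the tables.** The last futility rows (6/40 and 10/40) imply success at ≥7/40 and ≥11/40. At fixed n=40 these have exact type I error 0.0995 and 0.066. They fit 0.10 and not 0.05.

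**4. Printed futility boundaries alone.** The binomial path is followed patient by patient, and paths at or below a boundary are removed at each tabulated look. Expected n is the sum of each stopping n times its probability.

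| | Printed expected n (null/alt) | Futility-only expected n | P(reach 40), alt | Type I | Power |
|---|---|---|---|---|---|
| Cohort 1 | 17.7 / 18.3 | 19.1 / 36.0 | 0.817 | 0.069 | 0.801 |
| Cohort 2 | 19.2 / 21.0 | 20.3 / 36.6 | 0.821 | 0.054 | 0.789 |

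**5. A bound that needs no inferred rule.** Under futility-only stopping, success can be declared only at n=40. With 80% power, at least 80% of trials must therefore reach 40 under the alternative, and the rest use at least 10 patients. Expected n is at least 0.8 × 40 + 0.2 × 10 = 34. Conversely, an expected n of 18.3 allows at most (18.3 − 10)/(40 − 10) = 27.7% of trials to reach 40, and 21.0 allows at most (21.0 − 10)/30 = 36.7%. Power could be no higher than that.

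**6. What efficacy stop would fit.** Stopping as soon as 7 or 11 responses are in hand still gives 24.0 and 28.4 under the alternative, so the stop must be more aggressive. As an illustration, stop for efficacy when the predictive probability of final success exceeds 0.95, checked after every patient from n=10 with the plan's prior. This gives:
- Cohort 1: expected n 17.70/18.35 (18.348 before rounding), type I 0.087, power 0.808.
- Cohort 2: expected n 19.16/20.97, type I 0.073, power 0.802.

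That matches all four printed values, but the rule is inferred. With efficacy checks only at the tabulated looks, 0.95 gives 18.3/21.4 and 19.3/22.3, and no threshold matches.

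**7. Can 0.05 with 80% power describe the monitored design?** With the printed futility looks and final cut-offs of ≥8 and ≥12, power is 0.749 and 0.717 (type I 0.034 and 0.027). Optimising over all efficacy rules from n=10 with type I error at most 0.05 gives power ceilings of 0.7725 and 0.7784. It cannot, in either cohort.

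**The case against.** The strongest reply is that the two alphas have different jobs. The text ties 0.05 to sizing and 0.10 to the monitored design, and sizing more strictly than one monitors is permissible. Judged against its own 0.10/0.20 inputs, the printed rule does well: type I error is inside 0.10 in both cohorts, and power falls short only in Cohort 2, by 80 − 78.9 = 1.1 points, on an inferred success count. The arcsine formula is a standard approximation. The printed expected sizes are probably correct output of the full design with an efficacy stop, which would make this an omission and not a miscalculation. The primary analysis (8.2.3) is estimation with an exact 95% confidence interval, with no test against the null rates. Section 5.1.1 says Cohort 1 has enrolled its 40 patients and Cohort 2 is closed, so no further enrolment depends on the missing rule.

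Much of this stands. The choice of two alphas may be deliberate, the reported estimate and interval do not change, and the efficacy stop in step 6 is only an inference. But the plan never states the separate roles. It claims control of both error rates and reports operating characteristics, and these must belong to the rule it prints. The bound of 34 does not depend on the inference. Closed enrolment does not tell a reader whether an efficacy stop applied, or what count out of 40 was to be a success.

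**Conclusion.** The point holds and should be fixed. Under the alternative, the printed expected sizes are about half of what the printed rule gives: 18.3 against 36.0, and 21.0 against 36.6. An efficacy stop must lie behind them, and it is not in the plan. The 0.05/80% statement is an approximate fixed-sample calculation. Exact power at n=40 is 81.8% and 75.5%, and the statement does not describe the monitored design in either cohort.

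The futility-only figures assume looks exactly at the tabulated numbers, every patient evaluable at each look, and, for the error rates, success at one response above the last futility row. The Cohort 2 figures apply to the planned 40; that cohort closed early and its final number is not given. The futility tables themselves remain usable.

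**What to change.** 1. Relabel the 0.05/80% sentence as an approximate fixed-sample planning calculation, with exact power at n=40 of 81.8% (Cohort 1) and 75.5% (Cohort 2), or delete it.
2. State that the type I error of 0.10 governs the monitored design.
3. Do one of the following, according to what was intended:
   - If efficacy stopping was part of the design, print its rule, look schedule and final success count, with the type I error and power of that rule, and keep 17.7/18.3 and 19.2/21.0 if they are confirmed.
   - If only futility stopping applies, say so. Correct the expected sizes to 19.1/36.0 and 20.3/36.6, and report type I error 6.9%/5.4% and power 80.1%/78.9% for success at ≥7/40 and ≥11/40.

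Leave the futility boundaries as they are. The cost is SAP wording: no patients are added. The plan would rest openly on 0.10, which it already prints, and would show slightly under 80% power in Cohort 2 if only futility stopping applies.

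### Cohort 2's 40 patients give about 75.5% exact power, not 80%, for the one-sided 0.05 binomial test named in Section 8.2.2

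*Combined protocol and SAP*

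**What the plan says.** Section 8.2.2 (Sample Size) contains two statistical specifications.

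- **Sizing calculation.** It uses a "one-sample, one-sided binomial test, with Type I and Type II errors of 0.05 and 0.2, respectively". The rates are given as: "For Cohort 1, the null and expected response rates were taken to be 0.1 and 0.25, respectively" and "For Cohort 2, the null and expected response rates were taken to be 0.17 and 0.34, respectively". The result, for Cohorts 1 and 2 in that order, is: "The sample sizes were calculated to be 38 (which will be rounded to 40) and 40". No critical value is given, and nothing says whether the test is exact or approximated.
- **Monitoring design.** A Bayesian predictive-probability design follows, with 10 to 40 patients per cohort, the same pairs of rates, a beta(0.25, 0.75) prior, and type I and II errors of 0.1 and 0.2. It is described as monitoring both futility and efficacy, but only futility boundaries are printed. Their last rows treat 6 or fewer of 40 (Cohort 1) and 10 or fewer of 40 (Cohort 2) as futile. The printed expected sample sizes under the null and alternative are 17.7 and 18.3 for Cohort 1, and 19.2 and 21.0 for Cohort 2.

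Section 8.2.3 makes the primary analysis an estimate of the CR/CRi rate in each cohort with an exact two-sided 95% confidence interval.

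**The concern.** A one-sample binomial test with 40 patients has only a few usable cutoffs, so its attainable error rates move in steps. A sample size from a smooth approximation can fall where no cutoff delivers both stated errors. Cohort 1 has a two-patient margin from rounding; Cohort 2 has none. If the exact power is below 80%, a reader who takes the sizing sentence at face value would give a disappointing Cohort 2 result more weight as evidence against the combination than the test supports.

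**Working it through.** **Inputs, all from Section 8.2.2.** One-sided type I error 0.05 (z = 1.645); power 0.80 (z = 0.842); Cohort 1 rates 0.10 and 0.25; Cohort 2 rates 0.17 and 0.34.

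**Step 1: reproduce 38 and 40.** The arcsine formula is n = [(1.645 + 0.842) / (2·asin√p1 − 2·asin√p0)]².

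- Cohort 1: 1.0472 − 0.6435 = 0.4037, so n = (2.4865 / 0.4037)² = 37.94, giving 38.
- Cohort 2: 1.2451 − 0.8500 = 0.3951, so n = (2.4865 / 0.3951)² = 39.61, giving 40.

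Both stated sizes match. On this approximation Cohort 2 has nominal power 80.3% at n = 40. Other one-sided 0.05 calculations give different Cohort 2 sizes: normal score 36, continuity-corrected 42, Wald 49, exact 42.

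**Step 2: exact binomial tails.** The exact rule takes the smallest r with P(X ≥ r | p0) ≤ 0.05; power is P(X ≥ r | p1).

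| Cohort | n | Reject at | Type I error | Power |
|---|---|---|---|---|
| 2 | 40 | ≥11 | 0.0657 | 0.8500 |
| 2 | 40 | ≥12 | 0.0301 | 0.7552 |
| 2 | 42 | ≥12 | 0.0430 | 0.8165 |
| 1 | 38 | ≥8 | 0.0318 | 0.7687 |
| 1 | 40 | ≥8 | 0.0419 | 0.8180 |

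In Cohort 2 with 40 patients, a cutoff of 11 breaks the 0.05 limit and a cutoff of 12 falls short of 80% power. No non-randomised cutoff does both. The smallest size that does is 42. Cohort 1 would also have fallen short at 38, but rounding to 40 repairs it.

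**Step 3: the monitoring design.** The efficacy boundary is not printed, so this step rests on assumptions. I applied the printed futility rows, took final success as ≥7/40 (Cohort 1) and ≥11/40 (Cohort 2), and used the stated prior. Efficacy was checked after every patient from the tenth, stopping when the predictive probability of final success reached a threshold. Expected sample sizes are null / alternative.

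| Efficacy stopping | Cohort 1 expected n | Cohort 2 expected n | Cohort 1 type I / power | Cohort 2 type I / power |
|---|---|---|---|---|
| Printed in plan | 17.7 / 18.3 | 19.2 / 21.0 | not given | not given |
| None | 19.11 / 35.97 | 20.27 / 36.64 | 0.069 / 0.801 | 0.054 / 0.789 |
| Threshold 0.90 | 17.20 / 16.95 | 18.54 / 18.75 | 0.102 / 0.814 | 0.093 / 0.813 |
| Threshold 0.95 | 17.70 / 18.35 | 19.16 / 20.97 | 0.087 / 0.808 | 0.073 / 0.802 |
| Threshold 0.99 | 18.39 / 21.63 | 19.79 / 24.63 | 0.071 / 0.802 | 0.057 / 0.792 |

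Of the options tried, only 0.95 reproduces all four printed expected sizes, to within about 0.05.

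**The case against.** **The sizing sentence says binomial, not exact.** This is true, and 40 is a correct arcsine result rather than a slip. A score test at n = 40 rejects at 11: (0.275 − 0.17) / √(0.17 × 0.83 / 40) = 1.77, above 1.645. A mid-p test does too: 0.0301 + ½ × (0.0657 − 0.0301) = 0.0479. Both then have 85.0% power, but their actual type I error is 6.6%. The choice of test therefore moves the shortfall from power to type I error; it does not deliver 0.05 and 0.2 together. The exact minimum is only two patients more, which limits the size of the point.

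**The sizing test is not the operative rule.** This largely stands. The boundaries come from the predictive-probability design, and the primary analysis is an interval estimate. No 0.05 test with a cutoff of 12 appears in the analysis section.

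**A stronger reading.** A reader might infer that the printed futility tables also miss their stated errors, because running them alone gives 5.4% type I error and 78.9% power in Cohort 2, and 6.9% and 80.1% in Cohort 1. The documents do not support this. The tables belong to the design with stated errors of 0.1 and 0.2, so 0.05 is the wrong benchmark. Futility-only stopping also implies about 36 or 37 patients under the alternative, against the printed 18.3 and 21.0, so the design must include early stopping for efficacy. With that stopping reconstructed at 0.95, both cohorts meet 0.1 and 0.2.

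**Conclusion.** The point holds for the Cohort 2 sizing statement and is minor. For the named test at a true one-sided 0.05, 40 patients give 75.5% power, a type II error of 24.5% against the stated 20%. This follows from the stated rates and exact binomial tails, with no further assumption. Cohort 1 at 40 is adequate.

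The stated errors of the predictive-probability design are not shown to be missed. The approximate figures of 8.7% type I error and 80.8% power (Cohort 1) and 7.3% and 80.2% (Cohort 2) depend on the assumed 0.95 threshold and patient-by-patient looks. They are supported only by their match to the printed expected sizes.

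Section 5.1.1 says that Cohort 1 enrolled its 40 patients and that Cohort 2 closed to accrual on 1/8/2020. Cohort 2's enrolled number is not given, so its achieved power cannot be computed.

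**What to change.** Keep 40 per cohort and amend the wording of Section 8.2.2:

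1. State that 38 and 40 came from the arcsine approximation.
2. Give the exact one-sided 0.05 figures at n = 40: Cohort 2, ≥12 responses, type I error 3.0%, power 75.5%; Cohort 1, ≥8 responses, type I error 4.2%, power 81.8%.
3. Say that the predictive-probability design, with errors 0.1 and 0.2, governs the go/no-go decision.
4. Print that design's efficacy boundary and its type I error and power with efficacy stopping included. The study statistician should take these from the original design output; the 0.95 reconstruction is a check, not a substitute. The futility-only figures should not be used.

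The cost is a text change, with no added patients, procedures or analyses. The one downside is that the stated Cohort 2 power at 0.05 becomes slightly less favourable.
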